19.5 Secondary Analysis

The secondary objective is to evaluate the effect of flavoring on subjective effects (i.e. perceived harshness, satisfaction, liking, and relief of nicotine withdrawal symptoms) differences between matched free-base and salt-based e-liquids.

Each outcome will be modeled as a function of base, flavor, their interaction, prior combination, and a random subject effect using a linear mixed model. All model assumptions will be verified graphically and transformations will be applied as appropriate. An F-test about the interaction-term of base and flavor will be used to determine whether the impact of flavor on these subject measures differs between bases.

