8.2 Secondary Endpoint(s)

- Perceived harshness, satisfaction, liking, and relief of nicotine withdrawal symptoms.

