At visit one only, participants will be asked to complete several questionnaires including: Demographics (**Appendix E**), Smoking History (**Appendix F**), Time-line Follow Back to assess past 30 day tobacco product use (5) (**Appendix G**), Penn State E-cigarette Dependence Index (**Appendix H**), and Taste Preference (**Appendix I**). During each visit participants will be asked to report on the Minnesota Nicotine Withdrawal Scale (MNWS) and the strength of nicotine withdrawal symptoms (craving, irritability, difficulty in concentration, and restlessness) before and after product use (**Appendix J**). Participants will also rate their mood before and after product use (**Appendix K**). Satisfaction with and helpfulness of the product will be measured at the end of each session using an adapted questionnaire (**Appendix L**). Acute subjective responses to the effects of nicotine will also be measured using the Drug Effect Questionnaire (DEQ-5) after product use (**Appendix M**) as well as a questionnaire to assess a participant's craving to smoke (**Appendix N**). Puffing topography will be assessed with an eTop monitor after all blood draws are complete. At this time, subjects will be asked to puff on the assigned ENDS product ad lib with the eTop monitor. Participants will also be asked to complete the product evaluation scale, which assesses subjective effects such as liking and satisfaction, at visit four after experiencing each e-liquid solution (**Appendix O**). Additionally, participants will complete the Experimental Tobacco Marketplace product purchasing task (**Appendix P**). During the ETM, participants will purchase hypothetical tobacco products in an online store analog with an account balance determined by past 30 day-tobacco product use at Session 1. The product being sampled during the session will be available for purchase under four different price conditions. Other tobacco products will be simultaneously available at a constant price. Average time to completion using four price conditions is 8 minutes. Participants will also be asked to answer a series of questions regarding involving Sensory Measures (**Appendix Q**).

Table 3. Schedule of Procedures and Observations

Visit	#1	#2	#3	#4
Week	1	2	3	4
Nicotine Solution	E-liquid Solution #1	E-liquid Solution #2	E-liquid Solution #3	E-liquid Solution #4
Informed Consent ¹	X			

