Demographics and Smoking history (Appendix E) Timeline Follow-Back (Appendix G) Penn State E-Cigarette Dependence Index (Appendix H) Taste Preference (Appendix I), ENDS Dependence Scale (Appendix R)	X			
Vital signs	X	X	X	X
Blood Draw for Analytical Testing ²	X	X	X	X
Pregnancy Test (Urine)	X	X	X	X
Urine Sample (before and after 10min puffing session)	X	X	X	X
Puffing Topography	X	X	X	X
CO Pre and Post-Product Use ³	X	X	X	X
Minnesota Nicotine Withdrawal Scale (MNWS)(adapted) (Appendix J) Pre and Post Product Use	X	X	X	X
Positive Negative Affect Scale (PANAS) (Appendix K) Pre and Post Product Use	X	X	X	X
Satisfaction With and Helpfulness of the Products (Appendix L) Post Product Use	X	X	X	X
Drug Effect Questionnaire (DEQ-5) (Appendix M) Post Product Use	X	X	X	X
Modified Questionnaire of Smoking Urges (QSU-brief) (Appendix N) Post Product Use	X	X	X	X
Adverse Events	X	X	X	X
Concomitant Medications	X	X	X	X
Product Satisfaction Scale (Appendix O) Post Product Use				X
Experimental Tobacco Marketplace (ETM) (Appendix P)	X	X	X	X
Sensory Measures (Appendix Q) Post Product Use & Delay Discounting Task	X	X	X	X

1 Must be signed prior to any study related assessments or procedures.

2 See **Section 15** for Data and Specimen Banking

3 Expired CO will be measured before, and 3 minutes after the use of each product

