Appendix L

Product Evaluation Form: Satisfaction With and Helpfulness of the Product

Please answer the following questions about the Nicotine Solution you just used. Please mark an (X) in ONE box for each question					
	Much less than my regular device & e-liquid	A little less than my regular device & e-liquid	The same as my regular device & e-liquid	A little more than my regular device & e-liquid	Much more than my regular device & e-liquid
1. How good did it taste?					
2. How pleasant was it?					
3. How much did it relieve your urge to vape					
4. How was the effect of the e-Cig vapor on your:					
Tongue?					
Nose?					
Back of mouth and throat?					
Windpipe?					
Chest?					
5. How harsh was it?					
6. How much e-cigarette taste					

versus 'just air' did you get?					
	Much less than my regular device & e-liquid	A little less than my regular device & e-liquid	The same as my regular device & e-liquid	A little more than my regular device & e-liquid	Much more than my regular device & e-liquid
7. Was it embarrassing to use in front of others?					

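### The Section 19.5 model for relief of nicotine withdrawal does not adjust for the withdrawal score recorded before product use at each visit, which gives up precision at little saving

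*Combined protocol and SAP*

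**What the plan says.** Section 8.2 lists the secondary endpoints as "Perceived harshness, satisfaction, liking, and relief of nicotine withdrawal symptoms". Section 19.5 takes the same four outcomes, each "modeled as a function of base, flavor, their interaction, prior combination, and a random subject effect using a linear mixed model". The test follows: "An F-test about the interaction-term of base and flavor will be used" to judge whether the effect of flavor differs between salt and free-base liquids.

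Table 3 in Section 11 schedules, at visits 1 to 4, "Minnesota Nicotine Withdrawal Scale (MNWS)(adapted) (Appendix J) Pre and Post Product Use". A withdrawal score taken just before use therefore exists for every participant at every visit. The scales that can carry harshness, liking and satisfaction are scheduled after use only, for example "Drug Effect Questionnaire (DEQ-5) (Appendix M) Post Product Use".

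The documents do not say how relief is scored. It could be the post-use MNWS score, the pre-to-post MNWS change, or a post-use item in Appendix L such as "How much did it relieve your urge to vape".

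Section 11 also promises an analysis adjustment for participants whose pre-use plasma nicotine suggests they did not abstain. It gives no form for that adjustment and does not mention the withdrawal score.

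**The concern.** The interaction is a within-participant contrast, so its precision depends on visit-to-visit variation within a person. The random subject effect takes out a participant's usual level of withdrawal. It does nothing about a participant who arrives more deprived at one visit than at another. The protocol itself expects such variation: abstinence is 8 to 10 hours overnight, and Section 11 plans for some participants not adhering.

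The pre-use score measures that starting point directly, and it is taken before the visit's liquid is used, so it is a legitimate covariate. Leaving it out puts explainable variation into the residual. With at most 20 participants, and a sample size set on AUC rather than on any subjective outcome, a wider interval than necessary is worth avoiding when the data are already in hand.

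**Working it through.** **The plan's own figure.** Section 19.1 is the only sizing statement: n = 18, 80% power, two-sided 0.05, difference 700, SD 500 (ng/mL × min). The normal formula gives 2 × (1.960 + 0.842)² × 500² / 700² ≈ 8.01, rounded up to 9 per group, 18 in total. The exact t-test with 9 + 9 has 79.6% power. The figure reproduces, but it concerns AUC and says nothing about the secondary outcomes.

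**Inputs for this point**
- Model terms and interaction test: Section 19.5.
- Four visits, pre- and post-use MNWS: Section 11, Table 3.
- Williams design: Section 10.1. Maximum of 20 participants: Section 19.1.
- Within-participant pre/post correlation r: not in the documents, so varied from 0 to 0.9.
- Equal pre and post within-participant variances: assumed.

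**Variance per visit, with the post-use score set to 1**
- Post-use only: 1
- Change score: 2(1 − r)
- Post-use adjusted for pre-use: 1 − r²
- Adjusted relative to change: (1 − r²) / [2(1 − r)] = (1 + r)/2

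**Cost of estimating the slope.** With 20 participants there are 80 visits. Taking off 20 for subjects, 3 for liquids and about 3 for prior combination leaves 54 residual degrees of freedom. The adjusted variance is inflated by about 1 + 1/52 = 1.019.

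Example at r = 0.5: against post-use only, √(0.75 × 1.019) = 0.874. Against change, (1 + 0.5)/2 = 0.75, so the ratio is the same.

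**Simulation of the planned model.** Williams 4 × 4 design, 20 participants, prior-combination terms, subject fitted as a fixed effect so that only within-participant variation counts, 3,000 runs per value of r. Mean 95% CI width for the interaction, in within-participant SDs of the post-use score:

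| r | Post-use only | Change | Adjusted | Adjusted / post-use | Adjusted / change |
|---|---|---|---|---|---|
| 0 | 1.874 | 2.648 | 1.893 | 1.010 | 0.715 |
| 0.2 | 1.865 | 2.367 | 1.846 | 0.990 | 0.780 |
| 0.3 | 1.872 | 2.220 | 1.806 | 0.964 | 0.813 |
| 0.5 | 1.878 | 1.873 | 1.642 | 0.874 | 0.877 |
| 0.7 | 1.874 | 1.454 | 1.353 | 0.722 | 0.930 |
| 0.9 | 1.871 | 0.837 | 0.823 | 0.440 | 0.984 |

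The simulated ratios agree with the formulas to within about 0.003. With 18 participants the formulas give nearly the same ratios (0.965, 0.876 and 0.722 against post-use only at r = 0.3, 0.5 and 0.7).

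**Break-even.** Against post-use only, adjustment pays once (1 − r²) × 1.019 falls below 1, that is, for r above about 0.14. Against a change score it was narrower at every r tried, with the gain fading as r approaches 1.

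**The case against.** The best reply is that relief naturally means improvement from before to after use. On that reading the pre-use score is already inside the outcome, and a reader who infers that the plan discards it altogether goes beyond the text. This stands: only the covariate list is certain to lack it. It does not remove the point, because a change score fixes the slope on the pre-use score at 1, where adjustment estimates it. Over r = 0.3 to 0.7 that choice costs 19% down to 7% of the interval width.

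A second reply is that relief may be an Appendix L item, rated after use only, with no same-scale baseline. That stands too, and it is why the fix must begin by defining relief.

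A third is that the size of the gain rests on a correlation nobody has stated, and that at a low value there is almost nothing to gain over the post-use score. This is correct, so the result is given as a range.

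A fourth is that the planned adjustment for pre-use plasma nicotine addresses the same mechanism. It may do so in part, but it has no stated form and targets adherence, not the withdrawal score.

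Three stronger readings are tempting and are not supported:
- **Mood.** "Participants will also rate their mood before and after product use" might suggest that the same omission affects mood. Mood is not a secondary outcome in Section 8.2 or 19.5, so no mood model there lacks a baseline.
- **Bias.** Liquid order is randomized, so leaving out the covariate does not by itself bias the contrast.
- **A special penalty on the interaction.** Per participant, its variance is 4σ² against σ² for the base main effect, but extra residual variance multiplies both by the same factor. The proportional loss is the same.

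**Conclusion.** The point holds for one of the four secondary outcomes. As written, the Section 19.5 model for relief of withdrawal omits a covariate that is collected at every visit and that the random subject effect cannot replace. If relief is MNWS-based, adjustment narrows the interaction interval by about 4%, 13% and 28% against the post-use score alone, and by about 19%, 12% and 7% against a change score, at assumed correlations of 0.3, 0.5 and 0.7. The worst case examined is an interval about 1% wider than post-use only, at zero correlation.

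These figures assume equal pre and post variances and a correlation that the documents do not give. What is gained is precision and protection from chance differences in starting withdrawal between visits. Harshness, liking and satisfaction are measured after use only and are unaffected.

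**What to change.** In Section 19.5, define relief of nicotine withdrawal by the MNWS, naming the score and the post-use time point. Section 9 can be read as giving the scale at every blood-sampling time, while Section 11 says before and after use, so the time point needs stating.

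Then model the post-use MNWS score with base, flavor, their interaction, prior combination and random subject as now, and add the same visit's pre-use MNWS score as two terms: the participant's mean over the four visits, and the visit's deviation from that mean. The deviation term ensures that the within-participant slope is the one applied to the within-participant contrasts.

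The cost is a sentence or two in the plan and one or two degrees of freedom, with no new data or procedures. Writing it down before unblinding also closes off a later choice among post-use, change and adjusted scores.

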19.6 Exploratory Analysis

Exploratory analysis/analysis of exploratory aim: First, to quantify the relationship between purchasing and the price of e-cigarettes, the data will be fit to a modification of a model proposed by Hursh and Silberberg (2008):

$$Q = Q_0 + 10^{k(e^{-\alpha Q_0 C} - 1)},$$

where Q is amount of the commodity purchased, C is the price, Q_0 is the derived initial consumption without cost constraints (i.e., demand intensity and a secondary measure of abuse liability), k is the logarithmic range of the function, and α is the demand elasticity (i.e., sensitivity to price and the primary measure of abuse liability). Q and C are determined by the data and k is a set constant, leaving only Q_0 and α as free parameters to be fit. Second, the fit parameters, Q_0 and α will be compared with a 2 (nicotine type: salt- or free-based) X 2 (flavor: tobacco or unflavored) ANOVA to determine the abuse liability level of nicotine type, flavor, and the interaction between the two. Then, to analyze the level of substitution of alternative tobacco products, we will fit linear regressions for each product type. Slopes that differ from zero will be considered substitutes within each product availability condition. To compare the level of substitutability in the different product availability conditions, slopes will be compared using a 2 X 2 ANOVA.

Roswell Park Protocol No.: I 475819

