8.3 Exploratory Endpoint(s)

- Demand indices including intensity and elasticity of demand for each device sampled and substitution levels of alternative tobacco products.

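### Section 19.6 prints the demand equation with a plus sign that contradicts its own definitions, so a literal fit would mis-estimate the exploratory intensity and elasticity measures

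*Combined protocol and SAP*

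**What the plan says.** Section 19.6 states that "the data will be fit to a modification of a model proposed by Hursh and Silberberg (2008") and prints the result as "Q = Q_0 + 10^{k(e^{-\alpha Q_0 C} - 1", with the closing brackets following. The nature of the modification is not described.

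The symbols are defined next to the equation:

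- "Q_0 is the derived initial consumption without cost constraints"; it is named as demand intensity and as the secondary measure of abuse liability.
- "k is the logarithmic range of the function".
- "α is the demand elasticity (i.e., sensitivity to price and the primary measure of abuse liability").
- "k is a set constant, leaving only Q_0 and α as free parameters to be fit".

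The fitted Q0 and α are then compared by nicotine form and flavor in a 2 x 2 ANOVA. They supply part of the exploratory endpoint in Section 8.3: "Demand indices including intensity and elasticity of demand for each device sampled". Section 11 says that the sampled product is offered at four prices. No price levels, value of k or unit of Q are given, and the equation appears nowhere else.

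**The concern.** The definitions require a curve that starts at Q0 when the product is free and falls over k powers of ten as price rises, at a rate governed by α. A power term that is added to Q0 cannot do this. It is a quantity between 10^-k and 1 placed on top of Q0, so Q0 becomes a floor under demand and not its starting point.

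At stake are the two parameters through which the exploratory objective on abuse liability (Section 1.2) is answered. If they do not measure what the plan says they measure, the ANOVA can report a difference in intensity between salt and free-base liquids, or between flavors, that does not exist, and can misstate a real difference in elasticity.

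**Working it through.** The plan gives no numerical result for this analysis, so there is no figure to reproduce. The check sets the equation against its own definitions and then measures the effect of a literal fit.

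**Step 1: limits of the printed form** (exact for positive k, α and Q0; no assumed figures)

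- C = 0: the exponent is k(1 - 1) = 0, so Q = Q0 + 10^0 = Q0 + 1, not Q0.
- C very large: the exponent tends to -k, so Q tends to Q0 + 10^-k. Modelled purchasing stays above Q0 at every price.
- Maximum fall: (Q0 + 1) - (Q0 + 10^-k) = 1 - 10^-k. This is 0.90, 0.99 and 0.999 units for k = 1, 2 and 3, whatever Q0 or α.
- Logarithmic range for Q0 = 10 and k = 2: log10(11 / 10.01) = 0.041, not 2.
- Largest percentage fall at k = 2: 0.99 / 1.5 = 66% for Q0 = 0.5, 0.99 / 11 = 9.0% for Q0 = 10, and 0.99 / 51 = 1.9% for Q0 = 50.

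**Step 2: the form that satisfies the definitions**

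If the power term multiplies Q0, then Q = Q0 × 10^{k(exp(-α Q0 C) - 1)}. At C = 0 this equals Q0. As C grows it tends to Q0 × 10^-k, so the logarithmic range is exactly k. This form is inferred from the definitions in Section 19.6, not from the cited paper.

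**Step 3: effect of fitting the printed form literally**

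Assumptions, because the plan gives none of these figures: k = 2 or 3; four prices of either 0.25, 0.5, 1, 2 or 1, 2, 4, 8; true Q0 = 10 for both liquids; true α = 0.005 for liquid A and 0.02 for liquid B. Noise-free purchases were generated from the multiplicative form, and the printed form was fitted by least squares from many starting values.

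| k | Prices | Fitted Q0, A / B | Ratio (true 1) | Fitted α, A / B | Ratio B to A (true 4) | R2, A / B |
|---|---|---|---|---|---|---|
| 2 | 0.25 to 2 | 7.73 / 4.79 | 1.6 | 0.032 / 0.055 | 1.7 | 0.35 / 0.19 |
| 2 | 1 to 8 | 4.79 / 1.48 | 3.2 | 0.014 / 0.051 | 3.7 | 0.19 / 0.25 |
| 3 | 0.25 to 2 | 7.03 / 3.62 | 1.9 | 0.024 / 0.050 | 2.1 | 0.28 / 0.19 |
| 3 | 1 to 8 | 3.62 / 0.66 | 5.5 | 0.013 / 0.083 | 6.6 | 0.19 / 0.34 |

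The second row shows the mechanism. Liquid A's purchases are 7.99, 6.45, 4.34 and 2.19, with mean 20.97 / 4 = 5.24. The fitted curve is 5.54, 5.36, 5.13 and 4.94. Because the curve can move by less than one unit, fitted Q0 (4.79) settles just below the mean purchase. The mean depends on α, so a difference in α leaks into Q0. Refitting the same data with the multiplicative form returns the true Q0 and α in every case.

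**Step 4: dependence on the unit of Q**

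With true Q0 = 1, α = 0.1, k = 2 and prices 0.25 to 2, the one-unit cap does not bind and the printed form fits with R2 of about 1.0. It does so by sending Q0 towards zero (0.00004) and α to a very large value (2555), so that their product stays near the true 0.1. A good fit therefore does not make the parameters interpretable.

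**The case against.** **It may not be in the protocol at all.** The point turns on one symbol in a formula converted from PDF, and a multiplication sign could have been misread. This stands as a reason to check the source before changing anything. It does not clear the text as available, which is the only statement of the model.

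**It may be a typing slip that the code does not share.** The verbal definitions are coherent, no fitting code is in the documents, and an R2 near 0.2 would alert a careful analyst. This is plausible and keeps the point modest. But the plan sets no goodness-of-fit check for this model, and Step 4 shows that a near-perfect R2 can accompany meaningless parameters.

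**The model is described as a modification.** No intended modification makes Q0 + 1 equal to Q0, so this does not resolve the contradiction.

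Four stronger readings are tempting, and the documents do not support them:

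- A reader might infer that a true difference in elasticity would show up as a difference in intensity instead. In all four settings fitted α still separates the liquids; it is biased, and Q0 acquires a spurious difference as well.
- A reader might infer that Q0 and α cannot be estimated. Data generated from the additive form return that form's own parameters, so the equation is identifiable. Those parameters are simply not the quantities that the plan defines.
- A reader might take a 3-fold spurious intensity ratio as the size of the problem. That is one setting among several, and the plan gives no figures to choose between them.
- A reader might extend the doubt to the main results. The primary and secondary analyses (Sections 19.4 and 19.5) and the substitution regressions in Section 19.6 do not use this equation.

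**Conclusion.** The point holds as an error in the text as written. The contradiction is exact and needs no assumption beyond positive k, α and Q0: demand at zero price is Q0 + 1, the total fall is under one unit, and k is not the logarithmic range. A literal fit gives values of Q0 and α that are not demand intensity and price sensitivity.

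The practical size is uncertain. In the illustration, liquids of equal true intensity differ 1.6- to 5.5-fold in fitted Q0, and a true 4-fold ratio in α is fitted as 1.7- to 6.6-fold. Those ranges rest on assumed prices, k, Q0, α and noise-free data. They would change with the unit of Q. The consequence is confined to the exploratory demand indices and the ANOVA on them, and there is none if the source document and the code already use multiplication.

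**What to change.** Check the operator in the source document and in the fitting code. If it is a plus sign, replace it in Section 19.6 with multiplication: Q = Q0 × 10^{k(exp(-α Q0 C) - 1)}. Verify that the code returns Q = Q0 at C = 0. It would also help to state the value of k, the four prices and the unit of Q, so that the fitted parameters can be interpreted.

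The cost is one symbol, a few words of specification and a short code check. No further data are needed and no other analysis changes.

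### Exploratory substitution analysis (Section 19.6): the rule for calling a product a substitute has no sign, so a negative slope would also qualify

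*Combined protocol and SAP*

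**What the plan says.** Section 8.3 lists among the exploratory endpoints the "substitution levels of alternative tobacco products". Section 19.6 gives the analysis in three steps. First, "we will fit linear regressions for each product type". Second, the classification: "Slopes that differ from zero will be considered substitutes within each product availability condition". Third, a comparison across conditions: "To compare the level of substitutability in the different product availability conditions, slopes will be compared using a 2 X 2 ANOVA".

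Section 19.6 names no outcome, predictor, test, sidedness or significance level for these regressions. Section 11 describes the task that produces the data. On the test liquid: "The product being sampled during the session will be available for purchase under four different price conditions". On everything else: "Other tobacco products will be simultaneously available at a constant price". Participants spend from an "account balance determined by past 30 day-tobacco product use at Session 1". No section dealing with the marketplace task (1.2, 2, 8.3, 9, 11, 19.6, Appendix P) adds a sign condition or a category for negative slopes.

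**The concern.** Among the prices, only the test liquid's varies, so the slope for an alternative product is most naturally its change in purchases per unit increase in the test liquid's price. A substitute is a product people turn to when the test liquid gets dearer, which means a positive slope. A negative slope is the opposite finding. Taken literally, the rule gives both the same name.

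A negative slope is possible in this task. Suppose a participant has balance B, buys Q units of the test liquid at price C, and spends the rest on an alternative at constant price p. Purchases of the alternative are (B − Q·C)/p. If Q barely responds to price, this falls as C rises, with slope about −Q/p. The negative slope then reflects the balance being used up. Whether demand for these liquids is that inelastic is unknown beforehand. Section 19.6 itself sets out to estimate it, calling elasticity "sensitivity to price and the primary measure of abuse liability".

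At stake is the label that a reader would take away from a listed endpoint: which products replace the test liquid when its price rises.

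**Working it through.** The plan gives no figure for this test, so there is none to reproduce. What can be checked is how the rule behaves.

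**Inputs.**
- The rule: slope differs from zero, no sign (Section 19.6).
- Four prices for the test liquid, constant prices for the alternatives (Section 11).
- Assumed: a two-sided 5% test. Section 19.6 states no level; 0.05 is given only in Section 19.1, for the sample size.
- Assumed: normal approximation, critical value 1.96, with d = true slope divided by its standard error.

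**Formulas.**
- Rule as written: P(substitute) = [1 − Φ(1.96 − d)] + Φ(−1.96 − d).
- Rule with a sign: P(substitute) = 1 − Φ(1.96 − d).

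**Results.**

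| True slope (d) | As written | With a sign |
|---|---|---|
| −1 | 0.1701 | 0.00154 |
| −2 | 0.5160 | 0.0000375 |
| −2.80 | 0.7995 | 0.00000096 |
| 0 | 0.0500 | 0.0250 |
| +2.80 | 0.7995 | 0.7995 |

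For d = −1, the written rule gives Φ(−2.96) + Φ(−0.96) = 0.00154 + 0.16853 = 0.1701. Only the first term survives once a sign is required. At d = +2.80 the two rules differ by 0.00000096, so the sign costs no power for a true substitute.

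**Check by simulation.** A pooled least-squares slope was simulated with 20 participants at 4 equally spaced prices, independent errors with SD 1 and 20,000 runs per slope. Here Sxx = 20 × 5 = 100, so the standard error is 1/√100 = 0.1, and true slopes of −0.1, −0.2 and −0.3 are d = −1, −2 and −3. The written rule labelled 16.97%, 50.4% and 84.9% as substitutes; with a sign, 0.17%, 0.0% and 0.0%. A slope of +0.3 gave 84.3%, and 84.3% with a sign, so the written rule treats the two directions alike. A separate null simulation used per-participant slopes and a one-sample t-test (19 df, 200,000 runs). It labelled 5.08%, of which 2.57 points were negative slopes (2.57/5.08 = 50.6%).

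**Scale, for illustration only.** The Appendix P example screens show 4 product types (JUUL, patch, gum, lozenge). With 4 liquids that is 16 slopes. If price has no effect, the expected number of negative slopes called substitutes is 16 × 0.025 = 0.4. At a 1% level it is 16 × 0.005 = 0.08; at a 10% level, 16 × 0.05 = 0.8. The screens may not show the whole marketplace.

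**The case against.** The strongest reply is that this is a wording gap. Section 19.6 says that the purpose is to measure substitution, and a competent analyst who saw purchases fall would not report a substitute. A positive slope was probably intended. The endpoint is the level of substitution, which the slopes carry, and the 2 × 2 ANOVA uses them with their sign. The study is a pilot and the endpoint exploratory. All of this stands, and it is why the point is minor. It does not repair the rule: the sentence is the only one that turns slopes into a conclusion, and applied as written it gives the wrong one for a negative slope.

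A second reply is that the cross-price reading is inferred, and that Section 9 speaks of one fixed price for the tested product, which would leave no price to regress on. The reading is indeed inferred. But Section 11 is the more detailed text, and the demand curve in Section 19.6 also needs a varying price, so Section 9 does not rescue the rule.

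A third reply is that the probabilities are ordinary normal tail areas at chosen distances and say nothing about this trial. That is correct. They describe the rule and do not forecast the results. It is also true that, when price has no effect, a signed rule removes only half of the false labels (5.0% down to 2.5%).

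**Conclusion.** The concern holds. As written, the rule gives a significantly negative slope the same label as a significantly positive one. If the true slope is 1 to 2.8 standard errors below zero, the wrong label follows in about 17% to 80% of cases; with a sign it follows in at most 0.15%. These figures rest on an assumed two-sided 5% test and on the inferred regression of each alternative's purchases on the test liquid's price. How often negative slopes would arise cannot be found from the documents. The severity is minor: the effect stops at the verbal label for one exploratory endpoint.

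**What to change.** In Section 19.6, state that within each condition the purchases of each alternative product are regressed on the test liquid's price, and give the test and its level. Call a product a substitute only when its slope is significantly above zero. Report significantly negative slopes separately as not substitutes (complementarity or depletion of the account balance), and the rest as no detected price effect. In the same edit, reconcile the single fixed price in Section 9 with the four price conditions in Section 11.

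The cost is about two sentences, plus the Section 9 wording. No new data, visits or participants are needed, and no power is lost for positive slopes. The change should be made before the marketplace data are analysed, so that the sign convention is not chosen after the slopes are seen.
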